4.1.3. Missing data

All data will be analyzed as collected and missing values will not be imputed or replaced.

For the classification of treatment-emergent adverse events (TEAEs) and concomitant medication, the following imputation rules will be applied in a hierarchical order:

- If no start/end date information is available (i.e., no day, month, or year is available), the event/medication will automatically be classified as a TEAE/concomitant medication/procedure. AEs with a missing start time occurring on the day of vaccination will be set to a TEAE unless the end time of the event is before the vaccination time.
- For AEs/concomitant medications if only the event start year/end year is present and the start/end year is the same or after the year of the vaccination, then the event/medication will be classified as a TEAE/concomitant medication.
- If only the event/medication start/end year and month are present and the start/end year and month is the same or after the month and year of the date of the vaccination, then the event/medication will be classified as a TEAE/concomitant medication.

4.1.4. Multi-center studies

This is a multi-center trial in the United Kingdom. Data obtained at all sites will be combined into one data set prior to statistical analysis.

4.1.5. Multiple comparisons/Multiplicity

So far as no specific statistical hypothesis will be tested and only safety data will be evaluated, multiple adjustments are not applicable for this study.

4.2. Key definitions and principles

The following principles and definitions will be applied to all tables, listings, and figures (TLFs), unless otherwise specified, are described in [Table 2](#).

Table 2 Principles and definitions for all tables, listings, and figures

Principle/definition	Value
Baseline	
Is defined as the last available valid, non-missing observation for each subject on or before the vaccination of the prime dose at V01/Day 1. Repeat and unscheduled assessments will be included in the derivation of the baseline values.

Change from Baseline	
Is defined as difference between the results collected/derived at a post-baseline visit and baseline value.
 
The change from baseline value at each post-baseline visit will be calculated for continuous parameters using the following formula:
 $\text{Change from baseline} = (\text{Result at post-baseline visit}) - (\text{Baseline value})$ 
The change from baseline value will only be calculated if the specific post-baseline visit/time point result and the baseline value for the parameter are both available and will be treated as missing otherwise. In the data listings, the change values will be set to 'N/A' (not applicable) for pre-baseline assessments.

Study Day	
Is defined as the relative day of the event starting with the date of vaccination of the prime dose (the reference day) as Day 1 (there will be no Day 0).
 
The study day of events occurring before the vaccination of the prime dose will be calculated in the following way:
 $\text{Study day (before vaccination)} = (\text{Date of event}) - (\text{Date of Vaccination of Prime Dose})$ 
For events occurring on or after the vaccination will be calculated as:
 $\text{Study day (after vaccination)} = (\text{Date of event}) - (\text{Date of Vaccination of Prime Dose}) + 1$ 
Study days will only be calculated for events with complete dates and will be undefined for events that are 'Ongoing' at the end of the study.

Display Convention of Results	
Results will be center-aligned in all summary tables and left-aligned in all listings. Subject identifiers, visits, parameter labels, and comments may be left-aligned if required.

Descriptive Summary Statistics for Continuous Variables	
Descriptive statistics will include the number of non-missing values (n), arithmetic mean, standard deviation (SD), median, minimum (min), and maximum (max) values.
 
The minimum and maximum values will be displayed to the same decimal precision as the source data the arithmetic mean, median, values will be displayed to one more decimal than the source data, and the SD values will be displayed to two more decimals than the source data for the specific variable.
 
The maximum number of decimal places in the statistical report is four. If some descriptive statistical value has more than four decimal places after the application of the above-mentioned rules, this value will be rounded to four decimal places.
 
The appropriate precision for derived variables will be determined based on the maximum precision of the data on which the derivations are based, and statistics will be presented following the above-mentioned rules.

Descriptive Summary Statistics for Categorical Variables	
Descriptive statistics will include frequencies and percentages per category as well as clinical evaluations (normal, abnormal, and not clinically significant, abnormal, and clinically significant). The denominator in all percentage calculations will be the number of subjects in the relevant analysis population in the corresponding treatment group with non-missing data unless specifically stated otherwise.
 
Percentages will be rounded to one decimal place

Significance Test	
The default significance level will be 0.05 (5%); all tests are two-sided (where applicable) unless otherwise specified in the description of the analysis.

Confidence Intervals (CIs)	
The default CIs will be 95% and will be determined using the Clopper-Pearson method [6].

Principle/definition	Value
p-values	All p-values will be presented to 3 decimal places and values less than 0.001 or greater than 0.999 will be presented as <0.001 and >0.999, respectively.

4.3. Sample Size

The targeted sample size for each of the study cohorts was determined based on previous Phase 1 studies. Recruitment for GRT-R910 boost vaccination schedules will target enrolling 50 volunteers as follows:

- Cohort 1 (N=10, including 2 sentinels): 10 mcg GRT-R910 (after AstraZeneca) 2 doses, homologous prime-boost, booster dose will be 113 days (16 weeks) after the prime for adults ≥ 60 years of age.
- Cohort 2 (N=10, including 2 sentinels): 30 mcg GRT-R910 (after AstraZeneca) 2 doses, homologous prime-boost, booster dose will be 113 days (16 weeks) after the prime for adults ≥ 60 years of age.
- Cohort 3 (N=10): 10 mcg GRT-R910 (dose selected from Cohorts 1 and 2) after adenovirus-based vector vaccine, homologous prime-boost, booster dose will be 28 days after the prime for adults ≥ 60 years of age
- Cohort 4 (N=10): 10 mcg GRT-R910 (dose selected from Cohorts 1 and 2) after mRNA vaccine, homologous prime-boost, booster dose will be 28 days after the prime for adults ≥ 60 years of age.
- Cohort 6 (N=10): 10 mcg GRT R910 (dose selected from Cohorts 1 and 2) after mRNA vaccine, homologous prime-boost, booster dose will be 28 days after the prime for adults ≥ 18 to ≤ 59 years of age.

Sample size and power analysis for safety

The goal of the safety evaluation for this study is to identify safety concerns associated with product administration. The ability of the study to detect serious adverse events (SAEs) (see Section 11.1.2 of the protocol [2]) can be expressed by the true event rate above which at least 1 SAE would likely be observed.

For each group of 10 subjects, there is an 89% chance of observing at least 1 event if the true rate is 20% or higher.

Binomial probabilities of observing at least 1 event among groups of size 10 overall are presented in [Table 3](#) for a range of possible true adverse event rates [4]. These calculations provide a more complete picture of the sensitivity of the study design to identify potential safety problems with the vaccine.

Table 3 Probability (%) to Detect at Least 1 Adverse Event Under Different Incidence Rate

Incidence Rate (%)	Sample size = 10	Sample size = 20	Sample size = 30
0.01	0.10	0.20	0.30
0.1	1.00	1.98	2.96
1.0	9.56	18.21	26.03

Incidence Rate (%)	Sample size = 10	Sample size = 20	Sample size = 30
2.0	18.29	33.24	45.45
5.0	40.13	64.15	78.54
10.0	65.13	87.84	95.76
20.0	89.26	98.85	99.88

4.4. Randomization, Stratification, and Blinding

Since this is an open-label Phase 1 study, no randomization, stratification in randomization, or blinding will be performed. Thus, subjects and site staff will be unblinded as to subjects' cohort assignments.

4.5. Analysis Set

4.5.1. All Screened Subjects (AES)

The All Screened Subjects Analysis Set (AES) will contain all subjects who sign informed consent for this study. The subject screening and enrollment tables and listings will be reported using AES.

4.5.2. Intent-to-Treat (ITT)

The Intent-to-Treat Analysis Set (ITT) set will contain all subjects in AES who was not marked as screen failures. Subjects in the ITT analysis set will be analyzed according to the treatment assignment. The disposition tables and listings will be reported using ITT.

4.5.3. Safety Analysis Set (SAF)

The Safety Analysis Set (SAF) will contain all subjects in AES who received at least 1 dose of GRT-R910.

Summaries and analysis of safety data will be presented for the Safety Analysis Set. Subjects will be analyzed according to their actual treatment.

4.5.4. Immunogenicity Set (IMM)

The Immunogenicity Analysis Set (IMM) will contain all subjects in AES who received at least 1 dose of GRT-R910. For purposes of this SAP, it will be synonymous with SAF. However, further definition of the IMM set may be provided at a later time, as the immunogenicity analysis will be described in a separate standalone SAP, and performed by the sponsor.

4.5.5. Per Protocol Set (PPS)

The Per-Protocol Set (PPS) contains all subjects in ITT who received at least 1 dose of Investigational product (IP), with no major protocol violations. The major protocol violations that impact the Per-Protocol Set are detailed in the study deviation rules document. Prior to database lock, the sponsor will review the protocol deviations and categorize into minor or major protocol deviations and finalize the protocol deviations

Subjects will be analyzed according to their treatment assignment.

5. Subject Disposition

5.1. Subject Disposition

Subject screening and enrollment status will be summarized via AES; below information will be provided:

- Screened
- Enrolled - Enrolled represented the number of subjects who passed screening.
- Screen Failed
- Treated
- In Cohort 1 and 2 Consented to Booster Period

Subject disposition will be summarized by treatment cohort and total for the ITT using descriptive statistics (frequency and percentages).

The following characteristics will be summarized as subject disposition for the ITT:

- Number of subjects:
 - Completed the study
 - Discontinued the study
 - Ongoing
- Primary reason for discontinuation from the study and study drug
- Number of subjects in:
 - Safety Analysis Set
 - Immunogenicity Analysis Set
 - Per Protocol Immunogenicity Set

Also, the characteristics will be reported via data listing for the ITT.

5.2. Protocol Deviations

A protocol deviation is any noncompliance with the clinical trial protocol, any process that is noted in the protocol and refers to details in the protocol-specific manual of procedures (MOP) or GCP requirements, or any critical study procedures with specific instructions in ancillary documents referenced in the protocol such as a protocol-specific MOP.

Subject data will be examined for evidence of protocol deviations (PDs) to assess the protocol compliance. They are captured in the electronic data capture (EDC) system.

Before any reporting, each PD will be marked as major or minor. A major protocol deviation is considered synonymous to a significant deviation. A major protocol deviation is defined as a protocol or ICH/GCP deviation that affects the primary efficacy assessment, the safety or mental integrity of a subject, or the scientific value of the trial. A major protocol deviation can include nonadherence to inclusion or exclusion criteria or nonadherence to regulatory authority including International Council for Harmonization E6 (R2) [\[5\]](#) guidelines.

Major protocol deviations will be summarized by cohort and total for the ITT set using descriptive statistics (frequency and percentages).

All protocol deviations will be presented in a data listing, including the categorization of the deviation as important or not. Details of admission criteria deviations will be presented in a separate data listing. The significance of all protocol deviations will be determined by the sponsor.

6. Demographics and Baseline Characteristics

6.1. Demographics

Demographics will be summarized by cohort and total for the SAF analysis set using descriptive statistics.

The following data will be summarized:

- Age
- Sex
- If a female subject is Post-menopausal (percentages will be based on the number of female subjects)
- If a female is of child-bearing potential (percentages will be based on number of female subjects from cohort 6)
- If a female subject is of child-bearing potential, agreement to use of contraception on study per section 7.1 of the protocol
- If a female subject is of child-bearing potential, methods of contraception used
- Ethnicity
- Race
- Height (cm)
- Weight (kg)
- BMI (kg/m^2)

BMI will be calculated using the following formula: $BMI[\frac{\text{kg}}{\text{m}^2}] = \frac{\text{WEIGHT}[\text{kg}]}{(\text{HEIGHT}[\text{cm}]/100)^2}$.

Also, all parameters will be reported in a data listing for the SAF.

6.2. Baseline Disease Characteristics

The results of Nasal Swab SARS-CoV-2 PCR test will be summarized and reported via a data listing for the SAF.

6.3. Medical History

6.3.1. General Medical History

Medical history will be assessed at the Screening visit and then before GRT-R910 vaccination to ensure continued eligibility. Also, the medical history will be reviewed during the study to be sure that no changes took place since the previous clinic visit, phone call or other form of contact. The

Gritstone bio, Inc.
GO-009

Statistical Analysis Plan, Version 5.0
Date Issued: 09UN2023

interim medical history should include an assessment for new medical conditions and symptoms suggestive of an autoimmune disorder.

Medical history will be coded using the Medical Dictionary for Regulatory Activities (MedDRA) version to be delineated in the CSR.

Medical history will be summarized by SOC and PT within treatment group and total for the SAF. Additionally, medical history will be presented in a data listing.

No data will be imputed.

6.4. Inclusion and Exclusion Criteria

The inclusion/exclusion criteria will be reported by a data listing for the AES.

7. Treatments, Medications, and Recent Vaccinations

7.1. Prior and Concomitant Medications, and Recent Vaccinations

Administration of any medications, therapies or vaccines will be recorded on the appropriate DCF. Concomitant medications will include all current medications and medications taken in the 30 days prior to signing the ICF for the duration of the study. Medications reported in the electronic case report form (eCRF) are limited to those taken within 30 days prior to the first study vaccination and for 12 months after GRT-R910 vaccination. Prescription and over the counter drugs will be included as well as herbals, vitamins, and supplements. In addition, receipt of any non-study vaccines will be solicited for the entire duration of the study and reported in the eCRF.

Medications that might interfere with the evaluation of GRT-R910 should not be used during the trial reporting period (until approximately 12 months after GRT-R910 vaccination) unless clinically indicated as part of the subject's health care.

Recent vaccinations and concomitant medications and therapies will be summarized for the SAF by treatment group, anatomical therapeutic chemical (ATC) levels 1 and 2 and Preferred drug names as coded using the World Health Organization Drug Dictionary (version to be delineated in the CSR).

Additionally, any COVID-19 Emergency Use Authorization (EUA) will be recorded in CRF. If an EUA was reported, the usage of this medication should be considered as a major protocol deviation. Also, the case will be reviewed further to decide if subject will still stay on the study.

The rules for dates imputations described in [Table 4](#) will be applied to concomitant medications during this study. No other data will be imputed.

Table 4 Algorithm for missing dates imputations

Missing Date Type	Missing Date Description	Action
Start date	YYYY-MMM-UK	Assume YYYY-MMM-01, but if month and year are the same as the first study vaccination month and year, then assume the date of first vaccination

Missing Date Type	Missing Date Description	Action
	YYYY-UNK-UK	Assume YYYY-JAN-01, but if year is the same as the first study vaccination year, then assume the date of first study vaccination
	UNKN-UNK-UK	Assume the date of first study vaccination
Stop Date	YYYY-MMM-UK	Assume the last day of the month
	YYYY-UNK-UK	Assume YYYY-DEC-31
	UNKN-UNK-UK	Assign as 'Ongoing'

All concomitant medications and recent vaccinations will be reported via data listings. No partial dated will be imputed if the concomitant medications are considered as COVID-19 EUA; data queries will be sent to site to collect complete dates.

7.2. Study Vaccine Administration

Depending on the Cohort, study vaccination will be comprised of one or two intramuscular (IM) injections in the deltoid muscle of the subject's preferred arm. For Cohorts 1 and 2, initially subjects began the study only planning to receive one dose. In order to receive a booster dose, each subject needed to sign another ICF.

The number of doses received will be summarized for the SAF using descriptive statistics for qualitative variables. In addition, the vaccine administration data will be presented in a data listing.

8. Efficacy and Immunogenicity Analysis

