SAEs/AESIs Including PIMMCs/MAAEs/NOCMCs ¹³	X ¹⁴	X	X	X	X	X	X	X	X	X	X	X	X	X	X	X	X
Phone Visit ⁶			X	X					X	X							
Saliva Collection for Antibodies		X			X			X			X			X			

Abbreviations: AESI, adverse event of special interest; BP, blood pressure; d, day(s); ECG, electrocardiogram; HBsAg, hepatitis B surface antigen; HCV, hepatitis C virus; HIV, human immunodeficiency virus; MAAE, Medically Attended Adverse Event; NOCMC, New Onset Chronic Medical Condition; SAE, serious adverse event; PCR, polymerase chain reaction; PIMMC, Potentially Immune-Mediated Medical Condition; SARS-CoV-2, severe acute respiratory syndrome coronavirus 2; SCR, screening; Unsch, unscheduled

- Includes white blood cells (WBCs), hemoglobin (Hb), platelets (PLT), alanine aminotransferase (ALT), aspartate aminotransferase (AST), alkaline phosphatase (ALP), total bilirubin, creatine kinase (CK), serum creatinine, prothrombin time (PT)/international normalized ratio (INR), and activated partial thromboplastin time (aPTT)
- Includes WBC, Hb, PLT, ALT, AST, ALP, total bilirubin, CK, and creatinine
- Includes SARS-CoV-2 serology (N-specific) only
- If within 7 days after each vaccination (prime or boost dose)

- 5 If prior to Visit 11
- 6 Can be phone, text, or e-mail contact
- 7 A nasal swab for SARS-CoV-2 should be performed within 3 days of COVID-19 symptoms and repeated after 7 days.
- 8 ECG will be performed for subjects receiving booster dose in Cohorts 1 and 2. ECG data will include heart rate and RR, PR, QT, and QRS durations.
- 9 ECG will be performed before 1st and 2nd doses of vaccination.
- 10 Cardiac biomarker assessment will be performed for subjects receiving booster dose in Cohorts 1 and 2. Cardiac biomarker assessments will include troponin T, C-reactive protein (CRP), and erythrocyte sedimentation rate (ESR).
- 11 Cardiac biomarker assessment will be performed before 1st and 2nd doses of vaccination.
- 12 In case of second dose delay (allowed -3 days/+21 days), all safety visits (Visit 08 to Visit 12) will be scheduled based on the day of the second dose (e.g., Visit 08 will occur 1 day after delayed second dose and not on Day 114). All visits will shift based on the second dose without changing the time interval between 2 consecutive visits.
- 13 AESIs, including serologically or virologically confirmed SARS-CoV-2 infection and severity of COVID-19, PIMMCs, MAAEs, and NOCMCs will be collected from the time of first vaccination throughout the entire study.

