10.2 Laboratory Evaluations

10.2.1 Clinical Laboratory Evaluations

Subjects will be screened for HIV, hepatitis B surface antigen, antibody to hepatitis C virus and SARS-CoV-2. Results will be discussed with the subject. If a positive result occurs, the subject

will be referred for appropriate follow-up, and results will be reported as required by state law. These screening tests must be negative for the subject to be eligible to participate.

In order to be eligible for participation in the study and receipt of GRT-R910, the subject's clinical screening laboratory evaluations prior to each vaccination must be confirmed to meet the eligibility criteria as outlined in the Subject Inclusion Criteria (see [Section 7.1](#)).

The following tests will be performed by the local laboratory: WBC, Hb, PLT, ALT, AST, ALP, total bilirubin, CK, creatinine, PT/INR, aPTT, HIV serology, hepatitis B surface antigen, and hepatitis C antibody. Venous blood samples (approximately 17 mL) will be collected from each subject at the Screening Visit (Visit 00).

Clinical safety laboratory parameters evaluated after receipt of GRT-R910 will include WBC, Hb, PLT, ALT, AST, ALP, total bilirubin, CK, and creatinine.

Cardiac biomarker assessments will be performed for Cohorts 1 and 2 (subjects receiving booster dose) and Cohorts 3 and 4, and 6 to assess the potential risk of myocarditis with GRT-R910. Cardiac biomarker assessments include troponin T, C-reactive protein (CRP), and erythrocyte sedimentation rate (ESR).

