9.4. Cardiac biomarker

Cardiac biomarker assessment will be performed for Cohort 1 and 2 receiving booster dose only, and Cohort 3, 4, and 6.

Cardiac biomarker assessments include troponin T (cTnT), C-reactive protein (CRP), and erythrocyte sedimentation rate (ESR). The biomarker assessments will be summarized as mean, SD, median, min, max, and mean of actual value and as mean, SD, median, min, and max of change from baseline. An interpretation by study days table will be summarized for the SAF.

For subject with Early Termination (ET) visit, the ET visit will be set to the next protocol scheduled visit following ET within the specific study period. If the subjects completed all the scheduled visits and then discontinued, no mapping will be done.

All data will also be presented in a data listing for SAF.

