9.6. Electrocardiogram

Electrocardiogram (ECG) will be performed for Cohort 1 and 2 receiving booster dose only and Cohort 3, 4, and 6.

The ECG data will include heart rate and RR, PR, QT, and QRS durations. The investigator will be responsible for providing the interpretation of clinical significance for all ECG results.

The ECG assessments will be summarized as mean, SD, median, min, max, and mean of actual value and as mean, SD, median, min, and max of change from baseline. An interpretation by study days table in ECG will be summarized for the SAF

For subject with Early Termination (ET) visit, the ET visit will be set to the next protocol scheduled visit following ET within the specific study period. If the subjects completed all the scheduled visits and then discontinued, no mapping will be done.

All the ECG data will be listed.

10. Interim Analysis

No interim analysis was planned for this study; however, there may be unplanned interim analyses in light of the nature of Phase 1 study.

11. Changes in the Planned Analysis

- Efficacy analysis was added to the section 8.1
- Explained the occurrence of potential unplanned interim analyses in section 10.
- Calculation of solicited AE duration in section 9.1.2

12. References

1. ICH. Guidance for Industry (E9 Statistical Principles for Clinical Trials)
2. Gritstone bio, Inc. Clinical study protocol GO-009 Version 5.0 09 Feb 2023.
3. https://www.sas.com/en_us/home.html
4. Martin Bland Prof. of Health Statistics University of York, Detecting a single event

Gritstone bio, Inc.
GO-009

Statistical Analysis Plan, Version 5.0
Date Issued: 09UN2023

5. ICH. Guidance for Industry (Integrated Addendum to ICH E6(R1): Guideline for Good Clinical Practice E6(R2))
6. Clopper, C.J., and Pearson, E.S. (1934), "The Use of Confidence or Fiducial Limits Illustrated in the Case of the Binomial", *Biometrika* 26, 404-413
7. U.S. Department of Health and Human Services Food and Drug Administration Center for Biologics Evaluation and Research, "Toxicity Grading Scale for Healthy Adult and Adolescent Volunteers Enrolled in Preventive Vaccine Clinical Trials", 2007

Approved

Gritstone bio, Inc.
GO-009

Statistical Analysis Plan, Version 5.0
Date Issued: 09JUN2023

13. Appendices

Appendix 1

Table 6 Schedule of Study Procedures: Cohorts 1 and 2 – Subjects NOT receiving booster dose

Study Visit	V00	V01	V02	V03	V04	V05	V06	V07	V08	Unsch Visit	Early Term Visit

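### For boosted Cohort 1 and 2 subjects, the scheduled pre-prime cardiac tests conflict with their one-dose entry plan, and the SAP has no pre-booster reference if the pre-prime values are missing

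*SAP*

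**What the plan says.** - **Entry plan.** SAP 7.2: "For Cohorts 1 and 2, initially subjects began the study only planning to receive one dose". It continues: "In order to receive a booster dose, each subject needed to sign another ICF". SAP 5.1 plans to count the Cohort 1 and 2 subjects who gave that consent, but no number or date appears.
- **Who has cardiac tests.** SAP 9.4: "Cardiac biomarker assessment will be performed for Cohort 1 and 2 receiving booster dose only, and Cohort 3, 4, and 6". SAP 9.6: "Electrocardiogram (ECG) will be performed for Cohort 1 and 2 receiving booster dose only and Cohort 3, 4, and 6". Protocol Table 2, footnote 8: "ECG will be performed for subjects receiving booster dose in Cohorts 1 and 2". The schedule for Cohort 1 and 2 subjects without a booster (Protocol Table 1, SAP Table 6) has no ECG row and no cardiac biomarker row.
- **When the tests are done.** In the booster schedule (Protocol Table 2, SAP Table 7) both tests are marked at V01. Footnote 9 reads: "ECG will be performed before 1st and 2nd doses of vaccination". Footnote 11 says the same for the biomarkers.
- **Baseline.** SAP 4.2 sets baseline as the last valid value on or before the prime dose. Change from baseline "will only be calculated if the specific post-baseline visit/time point result and the baseline value for the parameter are both available" and is otherwise missing. SAP 4.1.3 imputes no missing values.
- **Output.** SAP Table 9 plans change from baseline for boosted Cohorts 1 and 2 in 14.3.5.4.3 (cardiac biomarkers) and 14.3.5.6.3 (ECG).
- **Purpose.** Protocol 10.2.1 says the biomarkers are measured "to assess the potential risk of myocarditis with GRT-R910".

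**The concern.** Whether a Cohort 1 or 2 subject falls under the booster schedule depends on receiving a booster. By SAP 7.2, that was not part of the plan when these subjects began. A subject on a one-dose plan at Day 1 would have had no cardiac test due before the prime, while the booster schedule says one was due. The same dependency applies to the marks at V04, V05 and V06.

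If the pre-prime value is absent, the SAP offers no other reference, and every change value for that subject is missing. These are the planned within-subject summaries of the tests that address myocarditis risk. Cohort 2 is the only 30 mcg group, so no other cohort can stand in for it.

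There is a second gap that does not depend on missing data. The only planned reference is pre-prime, so even with complete data no summary isolates the change across the booster dose, although both tests are scheduled immediately before it.

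**Working it through.** The plan gives no figure of its own on this point. The check sets the schedules against the baseline rule and counts what can be computed.

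**Inputs**
- ECG visits, booster schedule: V01, V04, V05, V06, V07, V10, V11, V12, V13, V14. That is 10 visits, 9 of them after the prime and 5 after the booster.
- Cardiac biomarker visits: the same list without V14 in Protocol Table 2 (8 post-prime, 4 post-booster), and with V14 in SAP Table 7 (9 and 5). The difference may come from how the tables were read; it matters here only for the count.
- Boosted subjects, N: not stated. The upper bound is 10 per cohort, 20 in all (Protocol Table 4).
- Boosted subjects with a pre-prime value, m: not stated, so varied from 0 to N.

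**Step 1. Change values computable under SAP 4.2.** Per parameter, computable = m × post-prime visits, out of N × post-prime visits. With N = 20 assumed:

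| m | ECG (9 visits) | Biomarkers, Protocol Table 2 (8 visits) |
|---|---|---|
| 0 | 0 of 180 | 0 of 160 |
| 5 | 5 × 9 = 45 of 180 | 5 × 8 = 40 of 160 |
| 10 | 10 × 9 = 90 of 180 | 10 × 8 = 80 of 160 |
| 20 | 20 × 9 = 180 of 180 | 20 × 8 = 160 of 160 |

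By SAP Table 7 the biomarker counts equal the ECG counts. For one cohort of 10, the ECG range is 0 of 90 to 90 of 90. The fraction is always m/N, so everything turns on a number that the documents do not give.

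**Step 2. Change values computable from V07.** Per parameter, computable = N × post-booster visits. For N = 20, ECG gives 20 × 5 = 100, and biomarkers give 20 × 4 = 80 (Protocol Table 2) or 20 × 5 = 100 (SAP Table 7). For one cohort of 10, the figures are 50, and 40 or 50. None of these needs a pre-prime value; they need only V07 and the later visit.

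**Step 3. What each reference measures.** V07 is Day 113, so 113 − 1 = 112 days, or 16 weeks, after the prime. With the window of −3 to +21 days it falls 109 to 133 days after the prime. V10 (Day 120) is 120 − 113 = 7 days after the booster but 120 − 1 = 119 days after the prime. Change at V10 from a pre-prime baseline therefore spans both doses, while change from V07 spans the booster alone.

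**Step 4. What can be reported either way.** Actual values from V07 on (6 ECG visits; 5 or 6 biomarker visits) and the interpretation-by-visit tables need no baseline.

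**The case against.** The strongest reply is that the plan does schedule a pre-prime baseline. Both booster schedules mark the tests at V01, and footnotes 9 and 11 name the first dose expressly. The current protocol describes Cohorts 1 and 2 as two-dose cohorts, with a single dose as an option for those unwilling to have a second (Protocol 4.3.1). This stands. A reader might infer from SAP 7.2 that no pre-prime test was scheduled, or that the change tables will be largely empty. The documents do not support either reading. They do not say when the second consent form was signed, how many signed it, or who had a V01 ECG or troponin. Late consent is suggested but not stated.

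A reader might also infer that the V07 results go unused. They do not: SAP 9.4 and 9.6 summarise actual values, tabulate interpretations and list all data. Nor would the report hide missing data, since continuous summaries show the non-missing n. What the actual-value summaries cannot give is the spread or the extremes of within-subject change across the booster, and for a troponin signal individual extremes matter more than a shift in means.

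It is also fair that these tests are not among the listed primary outcome measures, that the output is descriptive with at most 10 subjects per cohort, and that replacing the pre-prime baseline with V07 for everyone would discard V04 to V06 changes wherever V01 values exist. This last point shapes the fix.

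**Conclusion.** The concern holds as a conflict between passages plus a missing fallback. SAP 7.2 does not fit the V01 cardiac marks in Protocol Table 2 and SAP Table 7, and SAP 4.2 provides only one reference. The change-from-baseline content of 14.3.5.4.3 and 14.3.5.6.3 could rest on anywhere from 0 to 10 subjects per cohort. The low end requires that consent to the booster came after Day 1 and that no cardiac test was done at V01; the documents establish neither. The high end requires that the booster schedule was followed from V01.

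The lack of a planned within-subject change across the booster holds whatever that number is. The conflict and the missing fallback are certain; the eventual count is not. The point should be settled before the tables are produced, but it does not affect the listed primary outcome measures.

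**What to change.** 1. Reconcile SAP 7.2 with Protocol Table 2 and SAP Table 7: state when the second consent was obtained relative to the prime, and which schedule applied to boosted Cohort 1 and 2 subjects at V01 to V06.
2. In SAP 9.4 and 9.6, keep the pre-prime baseline wherever a value exists. Add a second, labelled reference for all boosted Cohort 1 and 2 subjects: the last value before the booster (V07), with change from it at V10 onward. This fits the division in SAP 9 of safety data into before booster and on or after booster.
3. In 14.3.5.4.3 and 14.3.5.6.3, report by cohort the number with a pre-prime value, and add a footnote that change after the prime dose cannot be assessed in subjects without one.

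The cost is SAP wording, one derived flag and a footnote, with no new data. The downside is a second reference taken about 16 weeks after the prime. It is not free of GRT-R910 exposure and should not be read as equivalent to the pre-prime baseline in Cohorts 3, 4 and 6; the label should say so.
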